## **11. REGULATORY CONSIDERATIONS**

### **11.1 Institutional Review of Protocol**

The protocol, the proposed informed consent and all forms of participant information related to the study (e.g. advertisements used to recruit participants) will be reviewed and approved by the Stanford IRB and Stanford Cancer Center Scientific Review Committee (SRC). Any changes made to the protocol will be submitted as a modification and will be approved by the IRB prior to implementation. The Protocol Director will disseminate the protocol amendment information to all participating investigators and research coordinators involved in the study.

### **11.2 Data and Safety Monitoring Plan**

The Stanford Cancer Center Data and Safety Monitoring Committee (DSMC) will be the monitoring entity for this study. The DSMC will audit study-related activities to determine whether the study has been conducted in accordance with the protocol, local standard operating procedures, FDA regulations, and Good Clinical Practice (GCP). In addition, the DSMC will regularly review serious adverse events and protocol deviations associated with the research to ensure the protection of human subjects. Results of the DSMC audit will be communicated to the IRB and the appropriate regulatory authorities at the time of continuing review, or in an expedited fashion, as needed.

### **11.3 Data Management Plan**

The Protocol Director, or his/her designee, will prepare and maintain adequate and accurate participant case histories with observations and data pertinent to the study. A Unique Study ID will be created for each patient to maintain patient confidentiality and the unique study ID will be used on case report forms (CRFs). The protocol director and his/her designee will keep the key linking patients with their unique study ID.

Study specific CRFs will document treatment outcomes for data analysis. Data from source documents are used to transcribe critical protocol data on CRFs. The REDCAP database system will be used to assist in data analysis and will be maintained by the protocol director or his/her designee. For any printed or paper CRFs, they will be kept in a locked office. Access to electronic study databases will be restricted by electronic password protection.

## **12. STATISTICAL CONSIDERATIONS**

### **12.1 Statistical Design**

This study is a phase 2 open label, fixed dose administration of CPX-351 to patients with HMA refractory or relapsed AML or higher risk MDS. In order to minimize the Phase II sample size in the event of an unfavorable response, a Simon two-stage minimax design will be followed. [name] is the biostatistician assisting with the project.

### **Sample Size Justification**

Using a desired significance of 0.05 (alpha; type I error) and power of 80% (beta 0.20; power=1-beta) with a two stage minimax design using  $p_0=0.20$  and  $p_A=0.40$ , a total of 33 patients will be accrued in this study.

Eighteen patients will be accrued during stage 1 and 15 patients during stage 2. For the first 18 patients, if no more than four out of 18 treated achieve the primary end point of CR/CRi after 2 induction cycles (i.e. response rate of 22%), then the regimen will be considered ineffective and the study will be terminated; if five or more of the 18 patients achieve a CR/CRi, the study will accrue to a minimum total of 33 patients.

### **Effect Size Justification:**

The null hypothesis ( $p_0=0.20$ ) is based on estimated predicted average CR/CRi rate of 20% based on several studies. In the retrospective review study by [23] outcomes of 61 patients with secondary AML who received traditional types of induction therapy were evaluated; of patients who had prior HMA therapy or revlimid, 32% achieved CR/CRi (compared to those who had induction chemotherapy after best supportive care; OR 1.13, 95% CI 0.04-0.42;  $p=0.001$ ). The median OS in this patient cohort was 3.7 months. In the retrospective study of outcomes of 74 patients with secondary AML after azacitidine treatment failure, 13 patients were noted to have been treated with “active therapies” after AZA failure; of 4 patients who received intensive chemotherapy, none responded [12]. In a study of outcomes of MDS after AZA failure, of 35 patients who received intensive chemotherapy, there was a 14% overall response with 8.9 months as the median survival ([13];  $p=0.04$  for patients in the intensive chemotherapy group for outcome compared to best supportive care). Given the wide range above, we estimate that the predicted response to traditional induction therapy in this group will be between 15-20% (lower than 32%) given the older age cohort in our study.

The alternative hypothesis of predicted CR/CRi response with CPX-351 in our study patients will be 40% ( $p_A=0.40$ ). In the preliminary Phase IIb data of CPX-351 induction therapy versus 7+3 therapy in newly diagnosed AML patients aged 60-75, the CR rate was 48.8% and the CRi rate was 17.9% with total response rate of 66.7%; patients with secondary AML had CR rate of 36.4% and CRi 21.2% with total response rate of 57.6%. Amongst the patients with secondary AML in the CPX-351 arm (N=33), 13 patients had prior hypomethylation therapy exposure and 16 had not; 4 patients had prior treatment with other agents. In the patients with prior HMA therapy receiving CPX-351, the CR rate was 23% (3/13) and CRi rate was 31% (4/13) with overall CR/CRi rate of 54% (7/13). We anticipate that the patients enrolled in our study will have an older age and include patients with MDS, and potentially lower CR/CRi rate. Thus our alternative hypothesis will conservatively be established at  $p_A=0.40$ .

#### **12.1.1 Randomization**

This is a fixed dose study of CPX-351. There will be no randomization.

#### **12.2 Interim analyses**

As described above, for the first 18 patients, if no more than four out of 18 treated achieve the primary end point of CR/CRi after 2 induction cycles (i.e. response rate of 22%), then the regimen will be considered ineffective and the study will be terminated; if five or more of the 18 patients achieve a CR/CRi, the study will accrue to a minimum total of 33 patients.

### **12.3 Descriptive Statistics and Exploratory Data Analysis**

We will describe the following for the group of patients in the study:

- We will describe age, sex, race/ethnicity, performance status of the patient group
- Descriptive analysis of how many patients have AML versus MDS; and how many patients have de novo AML versus secondary AML
- Descriptive analysis of prior therapies
- Descriptive analysis of IPSS score for patients with MDS at baseline
- Descriptive analysis of peripheral blood and blast percentage for the total group, and then subsets of AML and MDS at baseline
- Descriptive analysis of baseline ANC, hemoglobin, and platelet count at the time of study entry
- Descriptive analysis of cytogenetics and molecular features as available
- Baseline EF

### **12.4 Primary Analysis**

The primary outcome measures will be the following. Please refer to section 10 for details on definitions and time-frame of measurement.

- Safety data.
- Determining the response rate (CR + CRi) following up to two induction courses with CPX-351.

#### **12.4.1 Analysis Population**

- All patients enrolled in the trial who receive any dose of CPX-351 will be analyzed for safety
- All patients enrolled in the trial who receive any dose of CPX-351 will be analyzed for response (CR/CRi)
- Missing data for CR or CRi status will be considered as non-response as the conservative measure as a response cannot be definitely imputed in this population

### **12.4.2. Analysis Plan**

- To analyze the safety data, adverse events recorded using CTCAE 4.0 for each patient will be reviewed and totaled, for the total number of adverse events for each adverse event compared to total group of patients (rate of outcome of each adverse event in study population).
- The response rate will be calculated by adding the total CR + CRi (total number of CR + CRi for AML + CR for MDS) events after up to two courses of induction therapy, and comparing it to the total number of patients undergoing induction with CPX-351.

### **12.5 Secondary Analysis**

The secondary outcome measures will be the following:

- Determine the duration of remission following induction with CPX-351.
- Determine overall survival at 12 months.
- Determine the early induction mortality at Day 60 after 1st induction.

#### **12.5.1 Analysis Population**

- All patients who are initiated into the study will be analyzed for overall survival.
- All patients who receive at least one dose of CPX-351 will be included in the analysis of early induction mortality at Day 60.
- All patients who achieve CR will be included in the analysis of remission duration

#### **12.5.2 Secondary Outcomes: Analysis Plan**

Analysis of secondary outcome measures will be done by the following:

- The remission of duration will be calculated by counting the number of days from the date of remission until date of disease relapse for patients who achieve a CR (and CRi for AML). The average days of remission will be calculated to determine the median duration of remission.
- Induction mortality at Day 60 for patients for first induction therapy will be calculated by determining the number of deaths within the first 60 days, using Day 1 of the first induction therapy as the first day, compared to the total number of patients who have received any dose of CPX-351.
- The overall survival will be determined by the number of patients who are alive at 12 months compared to the number of patients who initiated into the study.

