#### **10.1.2 Measurement Time Points**

- Safety data will be assessed for 4 weeks following completion or discontinuation of treatment, or until initiation of new therapy, whichever one comes first.
- The response rate will be determined following the initial course of therapy (e.g. up to two courses of induction therapy with CPX-351).
- Overall survival will be determined at 12 months
- Early induction mortality will be determined on Day 60 after 1st induction (Day 1=first dose of CPX-351)
- Remission duration is from the start of response until disease relapse or death. A response will be classified as CR or CRi for AML, and CR for MDS

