##### **Response Criteria for AML:**

- Morphologic leukemia-free state is defined as having < 5% blasts by morphology from the Day 14 bone marrow aspirate following induction therapy. Day 14 bone marrows may be obtained +/- 3 days due to logistic purposes of institutional bone marrow processing. There should be no blasts with auer rods or persistence of extramedullary disease.
- Complete remission (CR) is defined as having < 5% blasts, with count recovery to platelets  $\geq 100,000/\mu\text{L}$  and ANC  $> 1000/\mu\text{L}$ . There should be no blasts with auer rods and no persistence of extramedullary disease. Patient should have transfusion independence.
- Complete remission with incomplete count (CRi) recovery is defined meeting all the parameters for CR, with the exception of platelets  $\geq 100,000/\mu\text{L}$  and/or ANC  $> 1000/\mu\text{L}$ .
- Partial response is defined as normalization of blood counts (ANC  $> 1000/\mu\text{L}$  and platelets  $> 100,000/\mu\text{L}$ ); a decrease of bone marrow blast percentage to 5-25%; and decrease of pretreatment bone marrow blast percentage by at least 50%; or  $\leq 5\%$  blasts with auer rods still present.
- Resistant disease is defined as failure to achieve a CR/CRi following up to two courses of induction therapy with CPX-351. It only includes patients surviving  $\geq 7$  days following completion of initial treatment with evidence of persistent leukemia by blood or bone marrow aspiration
- Death in aplasia: deaths occurring  $\geq 7$  days following completion of initial treatment while cytopenic; with an aplastic or hypoplastic bone marrow obtained within 7 days of death, without evidence of persistent leukemia
- Death from indeterminate cause: deaths occurring before completion of therapy or  $< 7$  days following its completion; or deaths occurring  $\geq 7$  days following completion of initial therapy but no blasts in the blood, but no bone marrow examination available
- Disease relapse after CR/CRi: bone marrow blasts  $\geq 5\%$  (not attributable to any other causes such as regenerating bone marrow; if equivocal after recent therapy whether from marrow regeneration, a repeat bone marrow biopsy at least one week later should be done); reappearance of blasts in the blood; development of extramedullary disease
- Overall survival is defined as the number/percentage of patients alive at 12 months (starting from date of entry into trial). Includes death from any cause.

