- Early induction mortality at Day 30 is defined as the number of patients who died during the first 30 days of treatment (with Day 1=first day of treatment) of the first induction
- Early induction mortality at Day 60 is defined as the number of patients who died during the first 60 days of treatment (with Day 1=first day of treatment) of the first induction
- Remission duration: is the number of days from remission until disease relapse (day when blasts > 5% are observed). It is defined for only patients who achieve a CR/CRi.
- Relapse free survival is defined for patients who achieve a CR/CRi in AML and is measured from the date of attaining remission until date of AML relapse or death from any cause.
- Event free survival is defined as time from date of entry into study until treatment failure, relapse from CR/CRi, or death from any cause (whichever occurs first). For patients who do not achieve a CR, EFS is defined as the point of progression or death (whichever comes first).

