**Response Criteria for MDS: Responses must last for at least 4 weeks as per IWG criteria**

- Complete remission is defined as  $\leq 5\%$  blasts with normal maturation of all cell lines; persistent dysplasia will be noted; there must be normalization of peripheral blood counts to: Hb  $\geq 11$  g/dL, platelets  $\geq 100,000/\mu\text{L}$ , ANC  $\geq 1000/\mu\text{L}$  with no blasts in the peripheral blood.
- Partial remission is defined as meeting all CR criteria except: bone marrow blasts are decreased by  $\geq 50\%$  over pretreatment value but still  $> 5\%$
- Marrow CR is defined as having bone marrow  $\leq 5\%$  myeloblasts and decrease by  $\geq 50\%$  over pretreatment
- Stable disease is defined as failure to achieve at least PR, but no evidence of progression for  $> 8$  weeks
- Treatment failure is defined as:
  - death during treatment; or
  - disease progression characterized by worsening of cytopenias; or
  - increase in percentage of bone marrow blasts;
  - or progression to a more advanced MDS FAB subtype than pretreatment
- Relapse after CR or PR: at least one of the following:
  - Return to pretreatment bone marrow blast percentage
  - Decrement of  $\geq 50\%$  from maximum remission/response levels in granulocytes or platelets
  - Reduction in Hb concentration by  $\geq 1.5$  g/dL or transfusion dependence
- Disease progression. For patients with:
  - Less than 5% blasts:  $\geq 50\%$  increase in blasts to  $> 5\%$  blasts
  - 5-10% blasts:  $\geq 50\%$  increase in blasts to  $> 10\%$  blasts
  - 10-20% blasts:  $\geq 50\%$  increase in blasts to  $> 20\%$  blasts
  - 20-30% blasts:  $\geq 50\%$  increase in blasts to  $> 30\%$  blasts
  - Any of the following:
    - At least 50% decrement from maximum remission/response in granulocytes or platelets
    - Reduction in Hb  $\geq 2$  g/dL
    - Transfusion dependence
- Overall survival is defined as the number/percentage of patients alive at 12 months (starting from date of entry into trial). Includes death from any cause.

- Early induction mortality at Day 30 is defined as the number of patients who died during the first 30 days of treatment (with Day 1=first day of treatment) of the first induction
- Early induction mortality at Day 60 is defined as the number of patients who died during the first 60 days of treatment (with Day 1=first day of treatment) of the first induction
- Remission duration: is the number of days from CR until disease relapse.

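### Remission duration: Section 12.5.2 uses an average to determine a median and gives ongoing remissions no value, and sections disagree on event, AML relapse date and population

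*Combined protocol and SAP*

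**What the plan says.** Section 12.5.2 takes the days from remission to relapse for patients with CR (and CRi in AML) and summarises them thus: "The average days of remission will be calculated to determine the median duration of remission". Section 4.1 (Follow-up) ends follow-up at death or 1 year after enrollment, leaves later marrows to the treating physician, lets the 1-year status come by telephone or correspondence, and collects remission duration only where possible.

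Other sections define the same endpoint differently:

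- **Section 10.1.2:** "Remission duration is from the start of response until disease relapse or death". On who counts as a responder: "A response will be classified as CR or CRi for AML, and CR for MDS".
- **Section 10.1.4, AML remission duration:** the count runs "until disease relapse (day when blasts > 5% are observed". Death is not named.
- **Section 10.1.4, AML relapse free survival,** a separately named measure: "measured from the date of attaining remission until date of AML relapse or death from any cause".
- **Section 10.1.4, AML relapse criteria:** marrow blasts of 5% or more, and also "reappearance of blasts in the blood; development of extramedullary disease".
- **Section 10.1.4, MDS:** remission duration "is the number of days from CR until disease relapse".
- **Section 10.1.1:** all patients with CR or CRi.
- **Section 12.5.1:** "All patients who achieve CR will be included in the analysis of remission duration".

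No section gives a censoring rule or a time-to-event method for this endpoint. Kaplan-Meier appears only in the account of Study 204. The missing-data rule in Section 12.4.1 covers CR/CRi status, not duration.

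**The concern.** The sentence in 12.5.2 is the only instruction for analysing this endpoint, and it cannot be carried out as written. It does not settle whether a mean or a median is reported. A patient in remission at 1 year has no relapse date and so no number to enter. Under the relapse-only wording, a patient who dies in remission has none either.

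The conflicts between sections are separate from that. For AML, relapse or death is exactly relapse free survival, so two different quantities share the name remission duration. An AML patient who relapses first in the blood or outside the marrow meets the relapse criteria but has a later date, or none, under the dating rule; a marrow count of exactly 5% also falls between the two. Applying 12.5.1 literally would drop CRi responders. In the reference data of Section 12.1, these were 4 of the 7 responders with prior HMA exposure.

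At stake is the reported duration figure and its comparison with other studies. The stage 1 rule (12.1, 12.2) and the step to a phase III trial (12.7) rest on response rate alone.

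**Working it through.** **The sections side by side**

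| Section | Event | Population |
|---|---|---|
| 10.1.1 | not stated | CR or CRi |
| 10.1.2 | relapse or death | CR or CRi (AML), CR (MDS) |
| 10.1.4 AML | relapse, dated by blasts > 5% | CR/CRi |
| 10.1.4 MDS | relapse | CR |
| 12.5.1 | not stated | CR |
| 12.5.2 | relapse | CR, and CRi for AML |

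On the event, 10.1.2 stands against 10.1.4 and 12.5.2. On population, 12.5.1 stands alone.

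**Number of responders.** The plan gives no figure for remission duration. Its sample size does reproduce: an exact search for the minimax design (p0 = 0.20, pA = 0.40, one-sided alpha 0.05, power 80%) returns 18 then 33 patients, stopping at 4 or fewer of 18, with type I error 0.0458 and power 0.801. Expected responders are p × [18 + 15 × (1 − probability of stopping at stage 1)]:

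- p = 0.20: 0.20 × [18 + 15 × (1 − 0.716)] = 0.20 × 22.25 = 4.45
- p = 0.40: 0.40 × [18 + 15 × (1 − 0.094)] = 0.40 × 31.59 = 12.6

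**Size of the possible bias (illustration).** Assumptions:

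- Durations are exponential with rate λ = ln 2 / median.
- Response is confirmed at about Day 42 (Section 4.1), or 1.4 months. With enrollment and treatment start taken as the same day, this leaves T = 12 − 1.4 = 10.6 months. T = 9.5 allows for response at 2.5 months, after a second induction.
- The true median is either 4 months (Section 2.1.1 has most poor-risk older patients relapsing within 3-6 months) or 6.9 months (the phase I study in Section 5.1.7, a different population).

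Formulas:

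- share ongoing at cutoff: S = exp(−λT)
- median among relapsers only: −ln[(1 + S)/2] / λ
- true mean: 1/λ
- mean with the cutoff counted as the end: (1 − S)/λ

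For a 6.9-month median and T = 10.6: λ = 0.1005, S = 0.345, and the relapser-only median is −ln(0.6725)/0.1005 = 3.95.

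| True median | T | Ongoing | Relapser-only median | True mean | Mean, cutoff counted as end |
|---|---|---|---|---|---|
| 4 | 10.6 | 15.9% | 3.15 | 5.77 | 4.85 |
| 4 | 9.5 | 19.3% | 2.98 | 5.77 | 4.66 |
| 6.9 | 10.6 | 34.5% | 3.95 | 9.95 | 6.52 |
| 6.9 | 9.5 | 38.5% | 3.66 | 9.95 | 6.12 |

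In all four rows S is below one half, so a plain median over all responders, with ongoing remissions kept at the cutoff, still targets the true 4 or 6.9 months.

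**Does the censoring date matter?** Suppose ongoing remissions are all censored at c months because no later marrow was taken, while relapses are dated when they occur. For t > c the Kaplan-Meier curve tends to exp(−λc) × [exp(−λt) − S] / [exp(−λc) − S]. Setting this to 0.5 with a true median of 6.9 and T = 10.6:

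- c = 0: 3.95
- c = 2: 4.5
- c = 4: exp(−λc) = 0.669, so exp(−λt) = 0.345 + 0.324 × 0.5/0.669 = 0.587 and t = 5.3
- c = 6: 6.3

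Censoring at an early last marrow therefore brings the bias back, even with Kaplan-Meier.

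**Will a median be reached?** Averaged over the two-stage design, given at least one responder and T = 10.6, more than half of the remissions are ongoing at cutoff in 18% of trials (20% response rate) or 10% (40% rate) if the true median is 6.9 months, and in 4% or 0.4% if it is 4 months.

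**The case against.** The strongest defence is that 12.5.2 names the median as the quantity to be reported, so the word average is loose drafting, and a plain median over all responders is unbiased. That stands as far as it goes. A reader might infer that the plan will report a biased duration, or that it excludes ongoing remissions. The documents support neither: no section says to leave those patients out, and 10.1.1 covers every patient with CR or CRi. But 12.5.2 does not select the favourable reading, and supplies no value for an ongoing remission.

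A reader might also infer that CRi responders will be dropped. Three sections, including the operative step in 12.5.2, say otherwise, so 12.5.1 is best read as a slip. The 4-of-7 figure comes from 13 secondary AML patients in another study.

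The dating parenthesis in the AML definition can be read as shorthand for the fuller relapse criteria just before it. That is plausible, and nothing in the documents puts a size on this point. A separate MDS relapse definition is not a contradiction.

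The survival medians after HMA failure in Section 2.1.5 do not describe remission length among responders, and they are not used here. Finally, the endpoint is descriptive and rests on few responders. That limits the importance of the point. The event conflict and the missing rule for ongoing remissions remain under any reading.

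**Conclusion.** Wrong as written, and worth fixing, on a descriptive secondary endpoint with no role in stopping. The average-for-median sentence, the absence of a value for remissions ongoing at 1 year, the conflict over death as an event and the CR-only population in 12.5.1 are all plain in the text. The narrower AML relapse date is a lesser inconsistency.

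The size depends on how the gap is filled. Leaving out ongoing remissions would turn a true 6.9 months into about 3.7 to 3.95, or a true 4 months into about 3.0 to 3.15; reporting a mean would answer a different question. Keeping every responder to the cutoff and taking a median gives no bias. These figures rest on exponential durations, the two assumed medians and windows of 9.5 to 10.6 months. The documents give no rate of death in remission, so the effect of the event conflict cannot be estimated.

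**What to change.** Replace the sentence in 12.5.2 with:

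> Duration of remission will be estimated by Kaplan-Meier from first documented response (CR/CRi for AML, CR for MDS) to relapse (criteria in 10.1.4) or death from any cause, as in 10.1.2. Patients alive without relapse are censored at the last date they were known to be relapse-free, including the 1-year status report. The median with 95% CI will be reported.

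Then:

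- Delete the word average, and add CRi for AML to 12.5.1.
- Use the same event in 10.1.2, 10.1.4 and 12.5.2, noting that for AML it equals relapse free survival. If the sponsor prefers relapse only, report cumulative incidence with death in remission as a competing event instead of the Kaplan-Meier estimate.
- Date AML relapse by the full AML relapse criteria in 10.1.4, and MDS relapse by the MDS criteria there.
- State whether follow-up for this endpoint continues through transplant in remission, which Section 4.1 permits, or is censored there.
- Record the relapse date and the last relapse-free date on the CRF.

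The cost is low: wording in four sections, two CRF dates and a small extra analysis. Sample size and the primary analysis do not change. The interval will be wide with about 4.5 to 12.6 expected responders, the median may not be reached, and relapse dates will stay imprecise because follow-up marrows are discretionary.

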### **Follow-up**

- Patients will be followed until death or up to 1 year following study enrollment
- Patient status report will be obtained at 1 year following study enrollment by either clinic visit or by telephone or correspondence or discussion with treating physician or evaluation of survival using the state/county/federal death reports. Patient status report will include survival status, and as possible: duration of remission, relapse/refractory status, and whether a new anti-leukemic therapy has been initiated.
- Clinic visits and laboratories will be done during follow-up time period at the discretion of the treating physician or institutional standard of care
- Bone marrow evaluations will be done as per standard of care or institutional guidelines at discretion of treating physician (example, any suspicion of relapse or change in counts without other explanation for lasting > 1 month)

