#### **4.4 Criteria for Removal from Study**

Patients will be discontinued from the study under the following circumstances:

- Completion of protocol
- Persistent disease with a lack of any response to treatment
- Persistent disease without achievement of CR/CRi despite two induction courses with CPX-351
- Relapsed disease: presence of > 5% blasts in the bone marrow following CR or CRi (note however patients who achieve morphologic leukemia free state after first induction but have disease relapse within ( $\leq$ ) 15 days will be eligible for a second course of induction)
- Patient non-adherence with protocol
- Administration of non-protocol consolidation or non-protocol salvage therapy
- Inter-current illness which in the judgment of the investigator affects assessment of clinical status to a significant degree, and requires discontinuation of protocol therapy for patient safety
- Withdrawal of informed consent by the study participant at any time. The patient will be classified as withdrawal of consent.

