**APPENDIX J: 2008 WHO Classification and Criteria for MDS**

Disease	Blood findings	BM findings
Refractory cytopenia with unilineage dysplasia (RCUD): (refractory anemia [RA]; refractory neutropenia [RN]; refractory thrombocytopenia [RT])	Unicytopenia or bicytopenia* No or rare blasts (< 1%)†	Unilineage dysplasia: ≥ 10% of the cells in one myeloid lineage < 5% blasts < 15% of erythroid precursors are ring sideroblasts
Refractory anemia with ring sideroblasts (RARS)	Anemia No blasts	≥ 15% of erythroid precursors are ring sideroblasts Erythroid dysplasia only < 5% blasts
Refractory cytopenia with multilineage dysplasia (RCMD)	Cytopenia(s) No or rare blasts (< 1%)† No Auer rods < 1 × 10  /L monocytes	Dysplasia in ≥ 10% of the cells in ≥ 2 myeloid lineages (neutrophil and/or erythroid precursors and/or megakaryocytes) < 5% blasts in marrow No Auer rods ± 15% ring sideroblasts
Refractory anemia with excess blasts-1 (RAEB-1)	Cytopenia(s) < 5% blasts† No Auer rods < 1 × 10  /L monocytes	Unilineage or multilineage dysplasia 5%-9% blasts† No Auer rods
Refractory anemia with excess blasts-2 (RAEB-2)	Cytopenia(s) 5%-19% blasts‡ Auer rods ±‡ < 1 × 10  /L monocytes	Unilineage or multilineage dysplasia 10%-19% blasts‡ Auer rods ±‡
Myelodysplastic syndrome—unclassified (MDS-U)	Cytopenias < 1% blasts†	Unequivocal dysplasia in < 10% of cells in one or more myeloid lineages when accompanied by a cytogenetic abnormality considered as presumptive evidence for a diagnosis of MDS (see Table 6) < 5% blasts
MDS associated with isolated del(5q)	Anemia Usually normal or increased platelet count No or rare blasts (< 1%)	Normal to increased megakaryocytes with hypolobated nuclei < 5% blasts Isolated del(5q) cytogenetic abnormality No Auer rods

Reference: [26]

**APPENDIX K: Patient Study Calendar  
Each Induction and Consolidation**

DAY	Screen	1	3	5	14+/-3	During  Count recovery or by Day 42+/-3	End of Active Treatment Phase  /Early Termination	30-day post last dose of study drug +/-3 days	1-year Follow-up (+/- 2 weeks) 
Informed Consent 	X								
Medical history	X								
Vital Signs 	X	X				X	X		
Physical Exam	X	X				X	X		
ECOG Perf Status	X	X 							
CBC with Diff	X	X			X 	X	X		
Chemistries 	X	X				X			
Urianalysis 	X								
CXR or CT Chest 	X								
ECHO or MUGA 	X								

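### 12-month overall survival is planned as a crude alive/entered proportion, with no censoring, confidence interval, median or rule for patients whose vital status is unknown

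*Combined protocol and SAP*

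**What the plan says.** Section 12.5.2 states: "The overall survival will be determined by the number of patients who are alive at 12 months compared to the number of patients" who entered the study. Section 12.5.1 fixes the denominator: "All patients who are initiated into the study will be analyzed for overall survival". Section 10.1.4 defines the endpoint in the same binary way, in the AML list ("Overall survival is defined as the number/percentage of patients alive at 12 months (starting from date of entry into trial") and again in the MDS list.

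On follow-up, section 4.1 states: "Patients will be followed until death or up to 1 year following study enrollment". It adds: "Patient status report will be obtained at 1 year following study enrollment by either clinic visit or by telephone". That sentence goes on to allow correspondence, the treating physician, or government death records as sources, and footnote 13 of the Appendix K calendar repeats this. The calendar column reads "1-year Follow-up (+/- 2 weeks", and after the visit 30 days from the last dose it schedules no contact until then. Sections 2.4.1 and 4.1 keep patients who stop treatment for lack of response under survival follow-up.

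Section 4.4 lists "Withdrawal of informed consent by the study participant at any time" as a reason for removal. It does not say whether vital status is still obtained afterwards. The only missing-data rule in the plan, in section 12.4.1, concerns CR/CRi. Kaplan-Meier appears only where results of an earlier trial (Study 204) are summarised.

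**The concern.** The formula has a fixed denominator and a numerator that needs positive knowledge that the patient is alive. It leaves no third category. A patient whose status cannot be established therefore pulls the estimate down by as much as a death would, and nothing in the plan would show the reader that this had happened.

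The proportion also ignores when deaths occur, so it yields no median. The historical series in section 2.1.5 are each summarised by a median survival (3.4, 5.6 and 4.3 months), and for the 5.6-month series the only survival rate quoted is at 2 years. No confidence interval is planned, although at this sample size the uncertainty is wide.

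**Working it through.** The plan gives no figure for 12-month OS to reproduce: no target, no precision and no loss rate. Its total of 33 comes from the response endpoint (section 12.1) and serves here only as the denominator.

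**Inputs**
- N = 33 if both stages accrue, or 18 if the trial stops after stage 1 (section 12.1).
- S(12), true 12-month survival: 28% in the decitabine-failure series and 8% in secondary AML after azacitidine failure (section 2.1.5).
- d, the probability that status becomes unobtainable by month 12, independent of survival. The documents do not give it; 5% to 20% is an assumption.

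**1. Weight of one unknown patient.** 1/33 = 3.0 points (1/18 = 5.6 points if the trial stops at stage 1).

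**2. Expected bias.** On the literal reading a patient counts as alive only if alive and known to be so. The expected estimate is S(12) × (1 − d), and the bias is −S(12) × d.

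| d (assumed) | Estimate at S(12) = 28% | Bias (points) | Estimate at S(12) = 8% | Bias (points) |
|---|---|---|---|---|
| 0% | 28.0% | 0 | 8.0% | 0 |
| 5% | 26.6% | −1.4 | 7.6% | −0.4 |
| 10% | 25.2% | −2.8 | 7.2% | −0.8 |
| 15% | 23.8% | −4.2 | 6.8% | −1.2 |
| 20% | 22.4% | −5.6 | 6.4% | −1.6 |

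The bias is proportional to S(12), so it grows if survival exceeds these benchmarks.

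**3. What this means in patients.** With exponential survival and loss, set λ = −ln S(12) and μ = −ln(1 − d). The expected number lost while alive is N × μ/(λ + μ) × (1 − exp(−(λ + μ))). At N = 33, S(12) = 28% and d = 10% this is 1.9 patients, of whom 33 × 0.28 × 0.10 = 0.92 would truly be alive at 12 months.

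**4. Illustration.** Take 33 patients: 9 known alive at 12 months, 3 of unknown status, and 21 deaths spread over the year in the shape of an exponential curve with S(12) = 28%.
- Crude proportion: 9/33 = 27.3%, exact 95% CI 13.3% to 45.5%. This is also the worst case.
- Kaplan-Meier, with the three censored at month 1, 3 or 6: 30.3%, 31.0% or 32.4%.
- Best case, all three alive: 12/33 = 36.4%.

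**5. Complete ascertainment.** Every patient has 12 months of planned follow-up, so there is no administrative censoring before that point. If every status is known, Kaplan-Meier at 12 months equals alive/N.

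**6. The visit window.** A status taken at week 50 and counted as 12 months errs upward. With exponential survival and S(12) = 28%, survival at week 50 is 0.28^(50/52) = 29.4%. The error is at most 1.4 points, reached only if every survivor were classified that early.

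**The case against.** The strongest reply is that the plan seeks vital status from several sources. Stopping treatment or leaving the clinic does not make a patient unknown: telephone, the treating physician or death records can still settle the matter, and non-responders stay under survival follow-up. A reader might infer that every patient who withdraws or is lost is counted as dead, or that everything depends on a single contact. The documents support neither. No section says that unknown status means death, and the missing-as-failure rule covers response only. The problem is confined to patients whose status remains unknown after all these sources have been tried.

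Nor is the direction of bias certain. A lost patient who does not appear in death records could be recorded as alive, which would bias OS upward, as the week-50 window also does. The downward figures are modest beside the sampling error: at 28% and N = 33 the 95% half-width is about 1.96 × √(0.28 × 0.72/33) = 15 points. Kaplan-Meier is not a cure either. If sicker patients withdraw, it overestimates survival, and if survivors are last seen at week 50, it carries that value forward to month 12.

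Finally, comparison with history is not ruled out, because two of the three series in section 2.1.5 also give 1-year rates (8% and 28%).

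All of this stands, and it limits the size of the point. It does not supply the missing rule, interval or median. The uncertain direction is itself a reason to write the rule down before data are seen.

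**Conclusion.** The point holds in limited form. The plan's estimator has no place for unknown vital status and, read literally, scores it as not alive. The expected downward bias is S(12) × d: 1.4 to 5.6 points at 28% and 0.4 to 1.6 points at 8%, for an assumed independent loss of 5% to 20%. It is zero if ascertainment is complete, and the direction could reverse if a negative death-record search is taken as survival. The documents do not show how many patients will be unknown, so none of these figures is a prediction.

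Independently of any loss, the analysis discards death times and plans neither a median nor an interval. That restricts comparison with the cited series but does not prevent it. OS is a secondary, descriptive endpoint with no hypothesis test, so the change is worth making because it is cheap; the trial's main conclusion does not depend on it.

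**What to change.** Amend sections 10.1.4 and 12.5.2 as follows:
- Define OS as time from study entry to death from any cause, censored at the last date known alive.
- Report the Kaplan-Meier 12-month estimate with its 95% CI, and the median OS (stated as not reached if the curve stays above 50% through 12 months). The crude proportion can remain as a supplementary line.
- State whether vital status is still obtained after withdrawal of consent and how such patients are classified. State also how a death-record search that finds nothing is classified.
- Report the number of patients with unknown 12-month status, with worst-case (all dead) and best-case (all alive) bounds.

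The cost is revised wording and one added CRF field for date of death or date last known alive, because the 1-year report in section 4.1 lists survival status but no such date. The field also shows how many survivors were last seen before the full 12 months. The main downside is that Kaplan-Meier assumes non-informative loss, which is why the bounds belong beside it. If every status is known, the 12-month figure does not change.
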